**(2) Rash scores compared with baseline: Changes in rash scores compared with baseline on days 3 and 5 after medication ;**

Affected area : The maximum affected area of each body part is 100% , and the affected area is locally scored according to the following table, 0-6.

Affected area	0	1-9%	10 - 29%	30 - 49%	50 - 69%	70 - 89%	90 - 100%
Local scoring	0	1	2	3	4	5	6

Clinical symptom score: The severity of each symptom is rated from 0 to 3:

Severity of illness	none	light	middle	Heavy
score	0	1	2	3
✓ The average severity of the affected area. Half-grade points can be recorded between each symptom grade, e.g. 2.5.				

Erythema: 0 = none; 1 = mild (barely visible, pink); 2 = moderate (clearly visible, dark red); 3 = severe (deep red or fiery red)

Papules: 0 = none; 1 = mild (barely noticeable raised areas); 2 = moderate (clearly visible raised areas but not prominent); 3 = severe (prominent raised areas)

Rash Scoring Scale:

Body Parts	erythema (0-3)	Edema / pimples (0-3)	Local scoring (0-6)	Body Parts Score

neck	( +	+	)	
trunk	( +	+	)	
Upper limbs	( +	+	)	
Lower limbs	( +	+	)	

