#### 3.2 Visit

Screening period/baseline: First visit D0, complete blood count, CRP, chikungunya nucleic acid and liver and kidney function tests

Treatment observation period: D1-D5, daily follow-up, filling in the CRF, collecting the complete blood count, CRP, and Chikungunya fever nucleic acid results on D5/Discharge day.

Follow-up after treatment; telephone follow-up was conducted on D7, D14, and D28.

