###### 4.1.1 Basis of diagnosis

- 1) Epidemiological data: living in Chikungunya fever endemic areas or having a travel history to epidemic areas within 12 days, and having a history of mosquito bites within 12 days before onset of the disease.
- 2) Clinical manifestations: Acute onset, with fever as the first symptom, rash appears 2 to 5 days after the disease, and severe pain in multiple joints.
- 3) Lab assessment: Chikungunya RNA detection from patient blood samples.

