###### 4.1.2 Diagnostic criteria

- 1) Suspected diagnosis: patients with the above-mentioned epidemiological history and clinical manifestations; or patients without epidemiological history but with the above-mentioned typical clinical manifestations.
- 2) Confirm the diagnosis: Patients with positive result of Chikungunya virus nucleic acid.

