##### 4.2 Inclusion Criteria

- (1) Meets the suspected or confirmed diagnostic criteria for chikungunya fever;
- (2) Symptom onset  $\leq$  3 days before enrollment;
- (3) Actual prescribed treatment aligns with the study's group assignment (Chinese medicine, Western medicine, or combined therapy);
- (4) Sign the informed consent form.

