#### 4.4 Source of Cases

At each research center, all eligible patients will serve as observation subjects for this cohort study. Patients will be assigned to respective observation cohorts based on their actual prescription status, with enrollment for each group continuing until the target number is reached.

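### The rash endpoint is change from a D0 baseline that can precede the rash, so it mixes new eruption with improvement and depends on how late patients enrol

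*Protocol*

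**What the plan says.** Section 6.2(2) sets the rash outcome as "Changes in rash scores compared with baseline on days 3 and 5 after medication". The program summary prints it in bold as one of three highlighted effectiveness outcomes. The text neither restricts it to patients with rash at D0 nor says how a D0 score of 0 is handled.

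The timing comes from three other places:

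- Section 4.1.1 says that "rash appears 2 to 5 days after the disease".
- Section 4.2 requires symptom onset no more than "3 days before enrollment".
- Section 3.2 fixes the baseline: "Screening period/baseline: First visit D0".

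There are two routes into the study under section 4.1.2. A suspected case is defined by clinical features, for example "patients with the above-mentioned epidemiological history and clinical manifestations", and the features listed in 4.1.1 include rash. A confirmed case needs only a positive RNA test: "Patients with positive result of Chikungunya virus nucleic acid".

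On the comparison, section 4.4 states: "Patients will be assigned to respective observation cohorts based on their actual prescription status". Section 10 compares quantitative outcomes between groups by t-test or analysis of variance. Section 9.1.4 names stratification, standardisation, multivariable methods and propensity scores in general terms. Section 6.1(5) records the time of onset.

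**The concern.** Change from baseline describes improvement only if there is something at baseline to improve. A patient enrolled before the rash erupts scores 0 at D0, and the D3 or D5 score cannot be lower than 0. For that patient the change shows whether a rash appeared and how far it had progressed, and it can never be negative. For a patient with rash at D0, the same quantity describes the course of an existing rash. Section 6.2(2) puts both into one mean.

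The mean also depends on where D0 falls in the illness. Treatment cohorts are formed by prescription, so patients in one cohort may present later than those in another. A difference in delay can then appear as a difference in rash outcome, in either direction, with no effect of treatment.

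**Working it through.** The protocol gives no expected share of patients with rash at D0 and no rash course, so there is no stated figure to reproduce. All distributions and rash curves below are assumptions. Days 3 and 5 after medication are taken as D3 and D5.

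**Step 1: the windows.** Enrolment is on illness day 0 to 3 (4.2). Rash starts on illness day 2 to 5 (4.1.1). Anyone enrolled on day 0 or 1 is before the rash window; the two windows overlap only on days 2 to 3. D3 falls on illness day 3 to 6, and D5 on illness day 5 to 8.

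**Step 2: share with no rash yet at D0.** This is P(rash day > enrolment day) among patients who get a rash, if rash is not needed for entry.

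| Timing assumption | Share |
|---|---|
| Both uniform, continuous | 1 - 1/18 = 17/18 = 94.4% |
| Both uniform, whole days | (4 + 4 + 3 + 2)/16 = 13/16 = 81.3% |
| Enrolment uniform, rash weighted 0.4/0.3/0.2/0.1 over days 2-5 | (1 + 1 + 0.6 + 0.3)/4 = 72.5% |
| Enrolment weighted 0.1/0.2/0.3/0.4 over days 0-3, rash uniform | 0.1 + 0.2 + 0.3×0.75 + 0.4×0.5 = 72.5% |
| Late enrolment and early rash, same weights | 0.1 + 0.2 + 0.3×0.6 + 0.4×0.3 = 60% |
| All enrol on day 3 | 66.7% (continuous uniform rash), 50% (whole-day uniform), 30% (early-weighted) |

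The limits are 0% (all rash on day 2, all enrolment on days 2-3) and 100% (all enrolment on days 0-1).

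**Step 3: allow for suspected cases.** Read literally, a suspected case has rash at entry. If a fraction s of patients enters that way, the share becomes (1 - s) × the value in step 2. Starting from 81.3% and 94.4%:

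- s = 25% gives 61% to 71%.
- s = 50% gives 41% to 47%.
- The share falls below one half when s exceeds 1 - 0.5/0.8125 = 38% or 1 - 0.5/0.944 = 47%.

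**Step 4: effect of delay with no treatment effect.** Assume the score is 6 at eruption and falls by 1.2 a day to 0 after 5 days, with rash day 2, 3, 4 or 5 equally likely.

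| Enrolled on illness day | Mean at D0 | Mean at D3 | Change at D3 | Mean at D5 | Change at D5 |
|---|---|---|---|---|---|
| 0 | 0 | (4.8+6)/4 = 2.7 | +2.7 | (2.4+3.6+4.8+6)/4 = 4.2 | +4.2 |
| 1 | 0 | (3.6+4.8+6)/4 = 3.6 | +3.6 | (1.2+2.4+3.6+4.8)/4 = 3.0 | +3.0 |
| 2 | 6/4 = 1.5 | 4.2 | +2.7 | (0+1.2+2.4+3.6)/4 = 1.8 | +0.3 |
| 3 | (4.8+6)/4 = 2.7 | 3.0 | +0.3 | (0+0+1.2+2.4)/4 = 0.9 | -1.8 |

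At D5 later enrolment looks better throughout. At D3 the change first rises and then falls.

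**Step 5: a different curve.** With continuous uniform rash timing, a one-day rise to a peak of 1 and a linear fade (4 days in all), the change for delays of 0, 1, 2 and 3 days is +0.17, +0.44, +0.61 and +0.33 at D3, and +0.61, +0.50, +0.22 and -0.11 at D5. The pattern is the same: falling at D5, non-monotonic at D3. Delay alone moves the score by up to about 0.4 of the peak at D3 and 0.7 at D5.

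**Step 6: two cohorts.** In the step 4 model, let one cohort have enrolment weights 0.4/0.3/0.2/0.1 over days 0-3 (mean delay 1.0 day) and another 0.1/0.2/0.3/0.4 (mean delay 2.0 days).

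- D5: 0.4×4.2 + 0.3×3.0 + 0.2×0.3 - 0.1×1.8 = 2.46, against 0.1×4.2 + 0.2×3.0 + 0.3×0.3 - 0.4×1.8 = 0.39. The difference is 2.07 points.
- D3: 0.4×2.7 + 0.3×3.6 + 0.2×2.7 + 0.1×0.3 = 2.73, against 0.1×2.7 + 0.2×3.6 + 0.3×2.7 + 0.4×0.3 = 1.92. The difference is 0.81 points.

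**The case against.** Four points can be made for the plan.

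- **A reader might infer that most patients have no rash at D0.** The protocol does not establish this. It gives two ranges and no distributions, and the suspected-case definition, read literally, brings in patients who already have rash. This objection stands, and the share must be left open.
- **A reader might infer that the endpoint measures eruption instead of improvement, or that later enrolment always flatters a cohort.** Neither is supported. For patients with rash at D0 the change does follow its course. Among patients with a D0 score of 0 the change equals the later score, which is still a measure of rash burden. The protocol calls the outcome a change in severity, not relief. The direction of the delay effect is consistent at D5 but not at D3.
- **A reader might infer that no adjustment is planned.** Section 9.1.4 does list adjustment methods, and onset time is collected. But the list is generic and does not name delay. Adjustment also cannot turn a change from 0 into a measure of improvement.
- **Covariates and zero baselines can be left to a statistical analysis plan.** That is fair for the covariate list. But the endpoint, its baseline, its time points and a default test are already fixed in the protocol, and the mixing follows from that definition.

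**Conclusion.** The point holds in a limited form. On the protocol's own windows, D0 precedes the rash in everyone enrolled on illness day 0 or 1 who later gets one, and in some enrolled on days 2 to 3. The change in these patients can only be zero or positive, so the section 6.2(2) mean mixes new eruption with improvement.

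The share affected is about 60% to 94% when enrolment is spread over days 0 to 3 under the weights tried and rash is not needed for entry. It is lower if enrolment clusters on day 3 or if many suspected cases enter with rash.

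The outcome also depends on onset-to-enrolment delay. In the illustrative model, a one-day difference in mean delay between cohorts produces a spurious difference of about 2 points at D5 and 0.8 at D3, on a peak of 6. These sizes rest on the assumed rash course. That delay shifts the result at both time points was seen under both curves tried. The endpoint should be changed, but the rash data remain usable.

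**What to change.** In section 6.2(2), split the outcome by D0 rash status:

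1. Among patients with a D0 score above 0, report change from baseline at D3 and D5.
2. Among patients with a D0 score of 0, report the incidence of new rash and the D3 and D5 scores.

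Compare cohorts in models adjusted for D0 score (where it is above 0) and for days from onset to D0, in place of an unadjusted t-test or analysis of variance of raw change. Enter delay as a categorical variable, or stratify by illness day. A linear term would not capture the D3 pattern. Name delay explicitly in section 9.1.4.

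Sections 4.1.1, 4.1.2 and 4.2 should also be reconciled: a suspected case, read literally, needs a rash that 4.1.1 does not expect before day 2, while 4.2 admits patients from day 0.

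No new data are needed. Onset time is recorded under 6.1(5), and the flow chart shows examinations at D0, D3 and D5. The cost is a smaller group for the improvement analysis, and some rewording.

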#### ■ VAS (Visual Analog Scale) pruritus score

No itching at all 0--1--2--3--4--5--6--7--8--9 — 10 Worst itching point

**(3) Complete fever reduction time: Complete fever reduction is defined as the body temperature dropping to 37.2°C or below after the first dose and maintained for 24 hours or more;**

(4) Nucleic acid negative conversion time;

(5) Time for single symptom to disappear;

(6) Overall symptom disappearance time;

(7) Time for white blood cell count to return to normal: the time from the first dose to the first observation of white blood cell count returning to normal;

(8) Time for platelet count to return to normal: the time from the first dose to the first observation of platelet count returning to normal;

(9) Incidence of Chikungunya-related complications: Proportion of patients with recorded AEs for Chikungunya-related complications (shock, DIC, encephalitis, acute liver injury, acute kidney injury, myocarditis, pericarditis, pneumonia, respiratory failure, rhabdomyolysis, acute pancreatitis) after the start of treatment.

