**Flow chart**

Stage	Screening Period / Baseline	Treatment observation period							Follow-up after treatment (telephone follow-up)		
		Visit 1 D0	Visit 2 D1	Visit 3 D2	Visit 4 D3	Visit 5 D4	Visit 6 D5	Visit X Before discharge	Visit 7 D7	Visit 8 D14	Visit 9 D28
Visit point (D, day)											
Informed consent form	×										
Chikungunya RNA test	×						×	×			
Epidemiological data	×										
General information and medical history	×										
Physical examination, vital signs	×				×		×	×			
Body temperature	×	Patient diary card for body temperature record									
Chikungunya Symptom Scale	×	×	×	×	×	×	×	×	×	×	×
Complication		×	×	×	×	×	×	×	×	×	×
Severe / critical illness		×	×	×	×	×	×	×	×	×	×
Laboratory tests	×						×	×			
Patient diary card collection	×						×	×			
Medication records	×	×	×	×	×	×	×	×			
Adverse Events		×	×	×	×	×	×	×	×	×	×

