### 5 Observation Cohorts and Treatments

#### 5.1 Treatment Allocation by Cohort

- Chinese Medicine Group: Chinese treatments, which may include herbal formulas (e.g., decoctions, granules) or acupuncture, tailored to their syndrome differentiation (e.g., heat-clearing, detoxifying, or dampness-resolving therapies).;

- Western medicine group: Patients receive only standard Western medical care, which may include antipyretics (e.g., acetaminophen), NSAIDs for pain, and supportive treatments (e.g., hydration);
- Integrated therapy group : receive both Chinese and Western treatments.

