## 6 Observation items and evaluation during the study period

### 6.1 Clinical characteristics

- (1) Patient demographic characteristics: gender, age, height, weight, ethnicity, etc.;
- (2) Epidemiological data: living in chikungunya fever endemic areas or having a travel history to epidemic areas within 12 days, and having a history of mosquito bites 12 days before onset of illness;
- (3) Past medical history and treatment history: past medical history, past medication history, surgical history, allergy history, history of adverse drug reactions, etc.;
- (4) Concomitant diseases and medications: disease name, treatment drugs, purpose of medication, method of medication, time of medication, etc.
- (5) The current illness situation: onset time, highest axillary temperature within 72 hours before consultation, and diagnosis and treatment.

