## 10 Statistical analysis

SAS version 9.4 or above was used for data statistical analysis.

All statistical tests were two-sided, and  $P < 0.05$  was considered to be statistically significant.

The description of quantitative indicators will calculate the number of cases (N), mean (Mean), standard deviation (SD), median (Median), minimum (Min) and maximum (Max). When comparing between groups, t-test or analysis of variance was used. The description of categorical indicators uses the number of cases (N) and percentage (%) of each category. When comparing between groups, chi-square test or Fisher's exact probability method was used. The Kaplan-Meier (KM) test was used to estimate the survival function and calculate the median time for time-to-event variables. The survival curves between different groups were compared based on the Log-Rank test, and the corresponding P value was calculated.

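### The fever endpoint in Section 6.2(3) ignores antipyretic and NSAID intake, which differs between cohorts by design, so drug-held fever counts as resolved mainly in the Western and integrated groups

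*Protocol*

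**What the plan says.** Section 6.2(3) counts complete fever reduction from "body temperature dropping to 37.2°C or below after the first dose and maintained for 24 hours or more". It is one of three effectiveness items in bold. Nothing in the definition refers to drugs taken during the 24 hours.

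The cohorts are formed by the treatment actually prescribed. Section 5.1 gives the Western cohort standard care "which may include antipyretics (e.g., acetaminophen), NSAIDs for pain, and supportive treatments (e.g., hydration"). The integrated cohort receives both kinds of treatment. The Program Summary restricts the Chinese medicine cohort to Chinese medicine; Section 5.1 describes the same cohort without that restriction.

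The Flow chart takes temperature after D0 from the "Patient diary card for body temperature record". The row "Patient diary card collection" is marked at D0, D5 and before discharge. The row "Medication records" is marked from D0 to D5 and before discharge. For concomitant treatment, Section 6.1(4) collects "disease name, treatment drugs, purpose of medication, method of medication, time of medication, etc".

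For time-to-event variables Section 10 plans Kaplan-Meier estimates, and states: "The survival curves between different groups were compared based on the Log-Rank test".

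**The concern.** Section 2 sets out to evaluate Chinese medicine. On this endpoint one comparator contains drugs given to lower temperature, and the endpoint is temperature. A patient who is still ill but spends 24 hours at or below 37.2°C on acetaminophen is scored exactly like a patient whose fever has ended. Because exposure follows from how the cohorts are defined, the misreading does not fall evenly: it advances the event in the Western and integrated groups and leaves it untouched in a group that takes no such drug.

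Two groups with the same course of illness could then show different fever curves. A real shortening of fever under Chinese medicine alone could be masked. In the integrated group, a gain over Chinese medicine alone could come from the antipyretic rather than from the combination.

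The methods in Section 9.1.4 (stratification, standardization, multivariate analysis, propensity score) adjust for differences between patients. They cannot repair an outcome that the comparator's own drug changes directly.

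**Working it through.** The Protocol states no sample size, fever duration, antipyretic use or power, so there is no figure of its own to reproduce. The check has a textual part and illustrations under stated assumptions.

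**1. Exposure set against the definition**

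| Cohort | Antipyretic or NSAID possible? | Can drug-held fever score as the event? |
|---|---|---|
| Western | Yes (Section 5.1) | Yes |
| Integrated | Yes (both treatments, Section 5.1) | Yes |
| Chinese medicine | No (Program Summary wording) | No |

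The last row rests on the Program Summary. The existence of a separate integrated cohort for patients on both treatments points the same way.

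**2. Effect on the median.** Assume an exponential time to true fever resolution with median m days in every group, so S(t) = 2^(−t/m). Assume that a share q of one group has drug-held fever scored as resolved on day 1. From day 1 on, the apparent proportion resolved is F(t) = 1 − (1 − q)·2^(−t/m). Setting F = 0.5 gives an apparent median of m·log2[2(1 − q)], but not below 1 day.

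| True median m | q | Apparent median | Resolved by D4: true | Resolved by D4: apparent |
|---|---|---|---|---|
| 2 days | 10% | 2·log2(1.8) = 1.70 | 75.0% | 77.5% |
| 2 days | 25% | 2·log2(1.5) = 1.17 | 75.0% | 81.2% |
| 2 days | 50% | 1 (floor) | 75.0% | 87.5% |
| 3 days | 10% | 3·log2(1.8) = 2.54 | 60.3% | 64.3% |
| 3 days | 25% | 3·log2(1.5) = 1.75 | 60.3% | 70.2% |
| 3 days | 50% | 1 (floor) | 60.3% | 80.2% |

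**3. Effect on the log-rank test.** Simulation with identical illness in both groups and an assumed 100 patients per group. Fever time is gamma with shape 2, and follow-up is cut at day 4. In one group only, each febrile day carries a probability p of a drug-held 24-hour spell. Without such spells the test rejects in 4–6% of runs, as it should.

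| p per febrile day | Rejection, median 2 days | Rejection, median 3 days |
|---|---|---|
| 5% | 13% | 20% |
| 10% | 34% | 60% |
| 20% | 86% | 98% |

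A second coding of the same model gave 15% / 41% / 94% and 24% / 68% / 99%. The steep rise comes partly from p applying afresh each febrile day, so these figures show direction and sensitivity and do not forecast the study.

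**4. Secondary point: the end of the diary.** If the card ends on day L, the latest fall that can be confirmed is on day L − 1, which is D4 for a D5 collection. The share that falls but is observed for less than 24 hours is S(L − 1) − S(L). At L = 5 under the exponential assumption this is:
- m = 1: 6.25% − 3.1% = 3.1%
- m = 2: 25.0% − 17.7% = 7.3%
- m = 3: 39.7% − 31.5% = 8.2%

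A D5 cut applies alike to all cohorts and does not by itself favour any of them.

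**The case against.** The strongest reply is that this is a choice of question and not an error. Antipyretics are named parts of the comparator, the study describes real-world care, and fever control on those drugs is part of what that care delivers. The 24-hour hold already screens out shorter dips. This stands: the stated definition answers a legitimate treatment-as-used question and should not be replaced. It does not answer whether Chinese medicine shortened the fever, and nothing in the Protocol warns the reader of the difference.

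It is also fair to object that the illustrative rates have no source and apply to one group only. They show how sensitive the comparison is, and no more. A statistical analysis plan that is not shown might add a rule on antipyretics, but the endpoint itself is fixed in the Protocol without one.

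A stricter definition has its own bias. NSAIDs taken only for joint pain would delay the event in the Western and integrated groups. Censoring at each dose would be worse, because needing a dose is tied to being ill.

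Some stronger readings are tempting, and the documents do not support them:
- A reader might infer that patients who leave early cannot be counted. Anyone whose temperature fell at least 24 hours before the last collection can be counted. The diary's span and the censoring rule are not stated, and the symptom scale is also marked at D7, D14 and D28, with content not given. Bias would need early leaving to differ between cohorts, and nothing in the Protocol says that it does.
- A reader might infer that antipyretic use goes unrecorded. Medication is recorded; only the definition leaves it out.
- A reader might take this as the study's leading time-to-event comparison. The Protocol names no primary endpoint and lists several such items.

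**Conclusion.** The concern holds for antipyretics and NSAIDs. The endpoint scores drug-held fever as resolved, and does so unequally across cohorts because of how they are defined. The expected direction is against Chinese medicine alone, provided that cohort takes no Western antipyretic, as the Program Summary says.

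The size cannot be fixed from the Protocol. Under the assumptions above, a modest share of drug-held fever is enough to move the apparent median by a quarter of a day to more than a day, and to raise the rejection rate well above 5% with no true difference.

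The diary point is minor: falls in the last 24 hours before collection are unconfirmed, and this matters for the comparison only if such leaving differs between groups.

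The rule should be settled before outcome data are examined, since a rule on antipyretics chosen afterwards would look driven by results.

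**What to change.** Keep the present definition in Section 6.2(3) and label it the treatment-as-used analysis. Add to the same item:

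- A supplementary analysis in which only a 24-hour spell at or below 37.2°C with no antipyretic or NSAID dose counts as the event, taken from the medication records already kept from D0 to discharge. Patients still taking such drugs stay at risk until their temperature record ends and are not censored at the dose.
- Both results side by side for all three cohorts, with a statement that they bracket the answer and that neither replaces the other.
- As a sensitivity check only, one question at the planned D7 call on whether fever returned, for patients whose card ends less than 24 hours after the fall.

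The change costs some wording, one extra analysis and one telephone question, and it alters no treatment. The supplementary analysis will have fewer events in the Western and integrated groups, and pain-only NSAID use will delay events there. It needs the timing of doses: Section 6.1(4) collects this for concomitant drugs, and the record should be confirmed to hold it for cohort treatment too. The D7 answer is recalled and cannot verify a 37.2°C reading, so it should not define the event.

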### 9.1.4 Control of confounding bias

The final data were controlled using statistical methods such as stratified analysis, standardization, multivariate analysis, and propensity score.

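### The log-rank comparison of fever resolution takes no account of how far into the illness patients start treatment, so a later-presenting cohort can look faster with no treatment effect

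*Protocol*

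**What the plan says.** Fever resolution is one of the three outcomes set in bold in the protocol's summary. Section 6.2 item (3) defines it as "body temperature dropping to 37.2°C or below after the first dose and maintained for 24 hours or more". The start of the clock is not written, but the wording implies the first dose. Items (7) and (8), white cell and platelet recovery, state it outright: for white cells, "the time from the first dose to the first observation of white blood cell count returning to normal". The symptom items, (5) and (6), give no origin.

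Section 4.2 requires symptom onset no more than "3 days before enrollment". The limit refers to enrolment, not to first dose. Section 4.4 sets the cohorts: "Patients will be assigned to respective observation cohorts based on their actual prescription status".

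Section 6.1(5) records "onset time, highest axillary temperature within 72 hours before consultation", so time from onset to first dose can be derived.

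On analysis, section 9.1.4 says that confounding is controlled by methods such as "stratified analysis, standardization, multivariate analysis, and propensity score", with no covariate named. Section 10 names Kaplan-Meier estimation for time-to-event variables and then: "The survival curves between different groups were compared based on the Log-Rank test". It mentions no stratification or covariate.

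**The concern.** An acute illness runs on a clock that starts at onset, whereas the fever outcome is in effect timed from first dose. A patient first dosed on illness day 3 may already be near the end of the fever, and one dosed on day 0 is not. If one cohort tends to present later, its patients can have less fever left to run at time zero whatever they are given.

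Prescription decides the cohort, and the protocol describes no randomisation, matching or stratified enrolment, so nothing in the design keeps illness day similar across cohorts. The entry window of up to 3 days is wide against a D1-D5 treatment observation period. At stake is whether a significant difference in fever resolution reflects treatment or only how early patients came for care. Symptom recovery is exposed in the same way if it is timed from first dose.

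**Working it through.** The protocol gives no sample size, power, effect size or fever-duration figure, so there is no figure of its own to reproduce. The check is whether the stated comparison keeps its 5% two-sided error rate when treatment does nothing.

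**Inputs from the protocol.** Entry 0 to 3 days after onset (4.2); cohorts by prescription (4.4); log-rank test, two-sided 0.05 (10).

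**Assumed inputs, not in the protocol.** Fever duration T from onset, its distribution and mean; the number per cohort; how the cohorts differ in illness day d at first dose; and that every patient is still febrile at first dose.

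**Step 1: the mechanism.** Let T be Weibull, S(t) = exp(-(t/λ)^k), with λ = mean/Γ(1+1/k). For a patient febrile at first dose, the remaining fever R = T - d has P(R > r) = S(d+r)/S(d).

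- k = 1 (constant hazard): P(R > r) = exp(-r/λ). This does not depend on d, so presenting later brings no advantage.
- k = 2 (rising hazard): P(R > r) = exp(-(2dr + r²)/λ²), which falls as d rises. The median of R is √(d² + λ² ln 2) - d. With mean 4 days, λ = 4/0.8862 = 4.514 and λ² ln 2 = 14.12. At d = 1 the median is √15.12 - 1 = 2.89 days; at d = 2 it is √18.12 - 2 = 2.26 days. One day's later start shortens the median by 0.63 day.

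**Step 2: error rate, Weibull durations.** Two cohorts of 100, no treatment effect, 600 simulated studies per setting. Entry-day probabilities on days 0, 1, 2, 3:

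- 1-day gap: (0.4, 0.3, 0.2, 0.1), mean 0.3 + 0.4 + 0.3 = 1.0, against (0.1, 0.2, 0.3, 0.4), mean 0.2 + 0.6 + 1.2 = 2.0.
- 0.4-day gap: (0.3, 0.3, 0.2, 0.2), mean 1.3, against (0.2, 0.2, 0.3, 0.3), mean 1.7.

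| Gap | Shape k | Unadjusted rejection, mean fever 3 / 4 / 5 days | Later cohort's median shorter by (days) | Stratified by d |
|---|---|---|---|---|
| 1.0 | 1 | 0.045 / 0.048 / 0.063 | about 0 | 0.043-0.057 |
| 1.0 | 2 | 0.658 / 0.532 / 0.393 | 0.58 / 0.68 / 0.74 | 0.048-0.057 |
| 1.0 | 3 | 0.965 / 0.912 / 0.808 | 0.85 / 0.90 / 0.90 | 0.048-0.053 |
| 0.4 | 1 | 0.053 / 0.047 / 0.058 | about 0 | 0.045-0.068 |
| 0.4 | 2 | 0.157 / 0.135 / 0.113 | 0.24 / 0.28 / 0.31 | 0.038-0.068 |
| 0.4 | 3 | 0.335 / 0.240 / 0.207 | 0.35 / 0.37 / 0.38 | 0.045-0.055 |

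With equal entry days the unadjusted test rejected in 0.042 to 0.062. The simulation standard error at 5% is √(0.05 × 0.95/600) = 0.009.

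**Step 3: a second distribution.** Gamma durations with mean 4 days, 150 per cohort, censoring at 5 days, times rounded up to 6 hours, 600 studies per setting.

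- 1-day gap (same entry probabilities as above): unadjusted rejection 0.712 (shape 4), 0.233 (shape 2) and 0.058 (exponential). Spurious median difference 0.67 day (shape 4) and 0.41 day (shape 2). Stratified: 0.048, 0.050, 0.057.
- 0.25-day gap, (0.25 each), mean 1.50, against (0.15, 0.25, 0.30, 0.30), mean 1.75: unadjusted 0.132 (shape 4) and 0.053 (shape 2). Stratified: 0.057, 0.045.

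**Step 4: dependence on being febrile at entry.** The entry criteria do not require fever at first dose. Suppose patients already afebrile were counted as resolved at time zero. With constant hazard and mean 4 days, the chance of being afebrile by day d is 1 - exp(-d/4): 0, 0.221, 0.393, 0.528 for d = 0 to 3. In the earlier cohort of the 1-day gap this gives 0.3 × 0.221 + 0.2 × 0.393 + 0.1 × 0.528 = 0.20; in the later cohort, 0.2 × 0.221 + 0.3 × 0.393 + 0.4 × 0.528 = 0.37. The later cohort would then look faster even with constant hazard.

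**The case against.** The strongest reply is section 9.1.4. The protocol commits to confounder control and collects onset time, and a covariate list is commonly left to a statistical analysis plan, which is not at hand. A reader might infer that the study will make no adjustment for illness day; the protocol does not support that. What remains is narrower: section 9.1.4 names no covariate, section 10 gives an unadjusted test, and a propensity model that left out illness day would not remove this bias.

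A reader might also infer that timing from first dose is itself the mistake. It is not. Starting follow-up at treatment start is usual in a cohort comparison, and the stratified results above keep that clock and hold the nominal error rate. Timing from onset without delayed entry would add time in which no event can count.

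A third reply is that the result is conditional, and this stands. The protocol does not show that cohorts differ in presentation day or that the recovery hazard rises with illness day. It also does not say which cohort would present later, so the direction of any bias is unknown. The largest rates come from mirror-image entry distributions chosen for illustration.

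Finally, extending the point to white cell and platelet recovery is tempting because their first-dose clock is explicit. Blood counts are scheduled only at D0 and at D5 or discharge, so those times are driven mainly by the visit schedule, and a day-for-day shift describes them poorly.

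**Conclusion.** The point holds in conditional form, for fever resolution and for symptom recovery if it is timed from first dose. The comparison stated in section 10 is open to bias from time between onset and first dose, and the general list in section 9.1.4 does not close the gap.

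With a recovery hazard that rises with illness day, a 1-day gap between cohorts gives false-positive rates of about 23 to 97% and a spurious advantage of about 0.4 to 0.9 day in the median. A gap of 0.25 to 0.4 day gives about 5 to 34%. With constant hazard and all patients febrile at first dose, or with equal entry days, there is no inflation. These figures rest on assumed fever durations (mean 3 to 5 days), assumed imbalances and 100 to 150 patients in each of two cohorts. They show what can happen, not what will. That stratification restores the error rate is firmer: it gave 0.038 to 0.068 in every setting examined, under both families of distribution.

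**What to change.** Keep the first-dose clock and write it into items (3), (5) and (6). In section 10, stratify the log-rank test for fever and symptom recovery by days from onset to first dose, or adjust a Cox model for it. Derive the variable from the onset time recorded under section 6.1(5). Use first dose rather than D0 as its end point, because the fever event can count only after the first dose. Include the variable in any propensity model used under section 9.1.4, and report its distribution by cohort.

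The onset time is already collected, so the change is one of wording. The price is a small loss of precision from the strata. It cannot be quantified here because the protocol gives no cohort sizes; where a stratum holds few patients from one cohort, the Cox adjustment is the more economical form.
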